5. STUDY DESIGN

5.1 STUDY TYPE & DESIGN

A prospective, controlled, observational study will be conducted at a single centre to examine the effects of 12 months of aromatase therapy on body composition, and other biomarkers of CVD burden. A total of 100 patients will be recruited. A separate group of 30 patients receiving tamoxifen therapy will also be recruited to serve as a comparator group for analysis of secondary endpoints.

5.2 SAMPLE SIZE CALCULATION

In studies reporting data on visceral adiposity in postmenopausal women using DXA, the standard deviation of patients' visceral adiposity ranged between 15-100cm² (14, 16,29, 30, 31).

As such, for the primary endpoint of change in visceral adiposity as in this study, we consider a 25% difference in visceral adiposity a clinically significant difference for this

study. As such, to detect a 25% difference in visceral adiposity tissue, assuming a standard deviation of 40cm^2 , a power of 80% and a two-sided significance level of 0.05, we will require recruitment of 40 participants in each study group. Factoring in a drop-out rate of 30%, we will require 100 participants in total.

With a sample size of 100, the study is adequately powered to detect a 25% difference in visceral adiposity tissue, assuming a standard deviation of 40cm^2 , a power of 80% and a two-sided significance level of 0.05. This number accounts for 30% attrition. Study recruitment is progressive so to ensure that the study will be adequately powered and so withdrawals can be accounted for.

Therefore, we aim to recruit a total of 100 patients (50 in each arm).

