4.3 OUTCOME MEASURES

Patients receiving each form of endocrine therapy (AI, tamoxifen, control) will be compared across groups with respect to the following primary and secondary endpoints.

1. Primary Endpoints

- Changes in visceral adiposity tissue at 12 months in women using aromatase inhibitors versus controls (DCIS/early stage breast cancer not requiring ET) as measured by DXA

Changes in subcutaneous adiposity tissue, fat and lean mass at 12 months in women using aromatase inhibitors versus controls (DCIS/early stage breast cancer not requiring ET) as measured by DXA

2. Secondary endpoints:

- Changes in body composition in women using tamoxifen at 12 months (measured by DXA, hologic) versus controls (DCIS/early stage breast cancer not requiring ET)
- Changes in glucose metabolism (measured by HOMA-IR, fasting glucose, insulin, c peptide, HbA1c and adiponectin, leptin levels) at 12 months
- Changes in lipid metabolism (measured by serum lipids) at 12 months
- Changes in abdominal aortic calcification (measured by DXA) at 12 months
- Changes in peripheral microvascular endothelial function (measured by EndoPAT) at 12 months
- Changes in degree of hepatic steatosis (measured by fibroscan and liver function tests) at 12 months
- Changes in visceral and subcutaneous abdominal fat volume and distribution (anthropometric measurements) at 12 months
- Changes in behaviour, mood and lifestyle (Assessment tools to determine any significant changes in appetite and exercise) at 12 months
- Changes in sex steroids at 12 months
- Changes in bone remodelling markers (ctx, p1np) at 12 months

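### Section 5.2 claims 80% power for a 25% difference in 12-month VAT change, but no reference mean is given and the SD offered is one of VAT level, so the claim is not established

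*Protocol*

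**What the plan says.** Protocol Section 4.3 lists as the leading primary endpoint "Changes in visceral adiposity tissue at 12 months in women using aromatase inhibitors versus controls". Section 5.2 says its calculation is "for the primary endpoint of change in visceral adiposity as in this study", so the link to change is explicit.

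The effect size is relative: "we consider a 25% difference in visceral adiposity a clinically significant difference". The SD set against it is absolute, since the study is sized "to detect a 25% difference in visceral adiposity tissue, assuming a standard deviation of 40cm^2". The error rates are "a power of 80% and a two-sided significance level of 0.05". The only support offered for the SD is the preceding sentence, which reports that in published studies "the standard deviation of patients' visceral adiposity ranged between 15-100cm²".

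From these inputs the section derives 40 per group. It then allows for 30% drop-out and settles on 100 in total, 50 per arm. Section 8.1 states that the analysis will adjust for age, comorbidities and baseline measurements.

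The protocol gives no mean VAT, no target in cm², no SD of change, and no correlation between baseline and 12 months.

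**The concern.** Two inputs do not fit the claim they support.

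First, a percentage effect and an SD in cm² cannot be combined without a mean to turn the percentage into cm². The section also leaves open whether the 25% is relative to baseline, relative to the control mean, or a difference between arms in percentage change.

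Second, the spread of VAT between women at one time is not the spread of their 12-month changes. The two are linked through the within-woman correlation, which is not mentioned. Nothing marks 40 cm² as an SD of change.

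At stake is the only justification given for 50 per arm. Section 5.2 declares a clinically important difference and asserts adequate power for it, but a reader cannot tell how large that difference is in cm² or what power the study has for it.

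**Working it through.** **Inputs from Section 5.2:** two-sided alpha 0.05 (z = 1.960), power 80% (z = 0.842), SD 40 cm², 1:1 allocation, 40 per arm before drop-out, 50 per arm recruited, 30% attrition. **Assumptions, not in the protocol:** mean VAT m, and baseline-to-12-month correlation r with equal variances at both times.

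**1. Reproduce the 40.** n per arm = 2 × (1.960 + 0.842)² × SD² / d². With d = 25 cm² and SD = 40 cm²: 2 × 7.849 × 1600 / 625 = 40.2. The t-test version gives 41.2. The stated 40 is reproduced to within rounding.

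In reverse, the difference detectable with 40 per arm is 2.802 × 40 × √(2/40) = 25.06 cm². Dividing by 0.25 gives an implied mean of about 100 cm². Allowing a tolerance of two patients per arm, the implied mean is about 98 to 104 cm².

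**2. Dependence on the unstated mean.** With d = 0.25 × m and SD held at 40, the n per arm needed (normal approximation) is:

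| Assumed mean (cm²) | 25% of mean (cm²) | n per arm |
|---|---|---|
| 80 | 20 | 63 |
| 90 | 22.5 | 50 |
| 100 | 25 | 41 |
| 120 | 30 | 28 |

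These rows take no credit for baseline adjustment. They show only how much the claim depends on the missing mean.

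**3. Level SD versus SD for change.** If 40 cm² is a level SD:

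- unadjusted change score: SD = 40 × √(2(1 − r)), which equals 40 only at r = 0.5;
- baseline-adjusted analysis: residual SD = 40 × √(1 − r²), which never exceeds 40.

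**4. Evaluable numbers.** 50 × 0.70 = 35 per arm. Power for 25 cm² with 35 per arm, two-sided t-test:

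| SD used | SD (cm²) | Power |
|---|---|---|
| As stated | 40.0 | 73% |
| Change score, r = 0.3 | 47.3 | 59% |
| Change score, r = 0.5 | 40.0 | 73% |
| Change score, r = 0.8 | 25.3 | 98% |
| Baseline-adjusted, r = 0.5 | 34.6 | about 85% |
| Baseline-adjusted, r = 0.8 | 24.0 | 99% |

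The detectable difference at 80% power with 35 per arm is 2.802 × SD × √(2/35) = 0.670 × SD. That is 26.8 cm² at SD 40, 23.2 cm² at SD 34.6 and 16.1 cm² at SD 24.0 (normal approximation).

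**The case against.** The strongest reply is that nothing has been miscalculated. Exactly 25 cm² is 25% of a mean of 100 cm², and the authors may have taken such a mean from their cited sources without reporting it. This stands. A reader might infer that 25% was mistaken for 25 cm², but the document does not show that. The defect is a missing reference mean, not wrong arithmetic in the 40.

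A second reply is that Section 5.2 names change as its endpoint, and that 40 cm² is simply assumed. It would indeed be too strong to say that the power claim refers to some other endpoint. That 40 cm² is a level SD is an inference, although from the only source the section offers.

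A third reply is that a level SD is conservative under the baseline adjustment planned in Section 8.1, because the residual SD cannot exceed it. This also stands, for a fixed difference in cm². It removes any argument from the SD alone that the adjusted analysis has less power than the stated SD implies. It does not supply the missing mean.

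Finally, a reader might conclude that a null result could not be interpreted. That goes too far: the estimate and its confidence interval can be set against 25% of the observed baseline mean, whatever the planning power was.

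**Conclusion.** The power statement is mis-specified and the direction of the error is open. The protocol does not establish 80% power for a 25% difference in 12-month VAT change. The calculation supports 25 cm² at SD 40 cm² with 40 evaluable per arm, and this matches the claim only if mean VAT is about 100 cm² and 40 cm² is the right SD for the endpoint.

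A mean below 100 cm² lowers power for 25%. So does a correlation below 0.5 if unadjusted change scores are analysed. Baseline adjustment with a positive correlation raises power for 25 cm². A reader might infer that the study is underpowered. The document does not support that, because it fixes neither the mean nor the correlation.

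At 35 evaluable per arm, power for 25 cm² is about 73% with the stated SD. With baseline adjustment it is about 85% at r = 0.5 and 99% at r = 0.8. Both r values are assumptions, as is equal variance at the two times. The point should be fixed, but it does not threaten the design.

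**What to change.** Rewrite Section 5.2 in the units of the endpoint:

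1. State the target as an absolute between-arm difference in 12-month VAT change in cm², or give the reference mean that makes that difference 25% and say what the percentage is relative to.
2. State whether 40 cm² is an SD of level or of change. If it is of level, replace it with an SD of change or a baseline-adjusted residual SD, with an assumed correlation, its source and a sensitivity range.
3. Restate power or the detectable difference for the 35 evaluable per arm that 50 recruited and 30% attrition leave, not for 50.

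The cost is one paragraph and a small table, with enrolment unchanged. The drawback is that the statement of 80% power for a 25% difference may have to be reworded or dropped.

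### Section 5.2 says 100 participants cover 30% attrition at 80% power, but on its own requirement of 40 per arm they cover 20%; covering 30% would need 116.

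*Protocol*

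**What the plan says.** Protocol section 5.2 sizes the comparison of aromatase inhibitor users with controls on visceral adiposity. The target effect is relative: "we consider a 25% difference in visceral adiposity a clinically significant difference". The standard deviation is 40 cm². No baseline mean and no difference in cm² is given. On these inputs, with "a power of 80% and a two-sided significance level of 0.05, we will require recruitment of 40 participants in each study group", the plan then allows for losses: "Factoring in a drop-out rate of 30%, we will require 100 participants in total".

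The next paragraph says that 100 gives adequate power for the same difference, SD, power and significance level, and adds: "This number accounts for 30% attrition". It also says that recruitment is progressive so that withdrawals can be accommodated. The section closes by fixing the target at 100, with 50 in each arm.

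Section 5.1 repeats the total of 100, and section 5.3 repeats 50 plus 50, referring back to this calculation. The synopsis figure of 130 is these 100 plus a tamoxifen group: "A separate group of 30 patients receiving tamoxifen therapy will also be recruited to serve as a comparator group for analysis of secondary endpoints".

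**The concern.** Three figures in one section cannot all hold: 40 per group required, 30% loss assumed, 50 per group recruited. Losing 30% of 50 leaves fewer than 40. The attrition allowance is stated twice and the claim of adequate power rests on it, so this is not a slip confined to one sentence.

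The comparison is the first primary endpoint (section 4.3), and section 5.2 is the protocol's only justification of sample size. If attrition reached the level that the plan itself assumes, a null result on visceral fat would be presented as coming from a study with 80% power when, on the plan's own premises, power would be lower.

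**Working it through.** **Inputs, all from section 5.2:** two-sided significance level 0.05; power 80%; SD 40 cm²; 40 per group required; attrition 30%; 50 per arm recruited. The difference is given only as 25%. Where a figure in cm² is needed, 25 cm² is used as an assumption; it corresponds to a baseline mean of 100 cm² (0.25 × 100 = 25).

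**Step 1: reproduce the 40 per group.** Normal approximation, n = 2 (1.960 + 0.842)² × SD² / difference². With SD 40 and 25 cm², n = 40.2, which rounds up to 41. The difference that gives exactly 40 is 25.06 cm². The stated 40 is therefore reproduced to within one participant, if the 25% means about 25 cm².

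**Step 2: what attrition does 100 cover?**
- Evaluable fraction needed: 40/50 = 0.80, so attrition of at most 20%.
- Remaining at 30% attrition: 50 × 0.70 = 35 per arm, 70 in total.
- Recruitment needed at 30%: 40/0.70 = 57.1, so 58 per arm and 116 in total (80/0.70 = 114.3, or 115 before equalising the arms).
- The common shortcut of multiplying by 1.30 gives 80 × 1.30 = 104, which is not 100 either.
- 100 is exactly 80/0.80.

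This step needs no outside figure and no absolute difference.

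**Step 3: power at 35 per arm, on the plan's premise that 40 per arm gives 80%.**
- Normal approximation: the standardised effect at 40 per arm is 1.960 + 0.842 = 2.802. At 35 per arm it is 2.802 × √(35/40) = 2.621. Power = Φ(2.621 − 1.960) = Φ(0.661) = 74.6%.
- Two-sample t-test: the difference giving exactly 80% at 40 per arm is 25.37 cm². At 35 per arm the same difference gives 74.4%.

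The loss due to attrition is thus about 5.5 percentage points.

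**Step 4: power under an assumed absolute difference (SD 40 cm², two-sided 0.05, t-test).**

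| Assumed difference | 35 per arm |
|---|---|
| 20 cm² | 54% |
| 25 cm² | 73.2% |
| 30 cm² | 87% |

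For 25 cm² the normal approximation gives 74.4% at 35 per arm. By t-test, 40 per arm gives 78.8% for that difference, not 80%. The difference detectable with 80% power (t-test) is 25.4 cm² at 40 per arm and 27.2 cm² at 35 per arm.

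**The case against.** The strongest reply is that recruitment is described as progressive, so withdrawals could be replaced. That would restore 40 per arm if it were a rule. But the protocol gives no replacement rule and no ceiling above 100, and 100 is expressly said to contain the 30% already. The sentence does not remove the contradiction.

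A second reply is that the section does not say when the 30% applies. The primary endpoint is at 12 months, while follow-up runs to 24 months (section 6.4). If 30% is the loss by 24 months, the loss at 12 months could be smaller and 40 per arm might remain. That is possible, but the section claims that the target covers 30%, and its own figures do not deliver this.

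A third reply concerns proportion, and it stands. A fall of about 5.5 points is modest beside the SD range of 15 to 100 cm² that section 5.2 itself reports. The analysis in section 8.1 also adjusts for baseline and uses longitudinal models, which this unadjusted calculation ignores.

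A reader might infer that attrition takes power from 80% down to 73%. The documents do not support that as a like-for-like comparison. The 73% needs an absolute difference of 25 cm², which the protocol never states, and with that difference and a t-test the plan's own 40 per arm gives 78.8%. Part of the gap therefore comes from the assumed difference and the choice of test. Nor do the documents show that the study is underpowered whatever happens: with attrition of 20% or less, the required 40 per arm are retained.

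**Conclusion.** The attrition statement is wrong as written. On the plan's own requirement of 40 per arm, 100 participants allow for 20% attrition. At 30%, 35 per arm remain, and retaining 40 would take 116, which is 16 more than planned. The 30 tamoxifen patients do not help, because they are outside the primary comparison.

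This arithmetic rests on no assumption. The power figure does. If 40 per arm gives 80%, power at 35 per arm is about 74–75%. It is 73% by t-test if the 25% is taken as 25 cm² with SD 40 cm². Since the absolute difference is not stated, the range matters: 54% for 20 cm² and 87% for 30 cm². For the difference that reproduces the plan's 40 per group, about 73–75% is a fair summary, so the chance of missing that difference is about 25–27% and not 20%.

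**What to change.** Keep the target of 100 and correct section 5.2:

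1. In the sentence "Factoring in a drop-out rate of 30%, we will require 100 participants in total", change the drop-out rate to 20%.
2. Delete "This number accounts for 30% attrition". In its place, state that at 30% attrition 35 per arm remain, with about 73–75% power for the planned difference.
3. Make the sentence asserting adequate power with 100 participants conditional on attrition of no more than 20%.
4. State the absolute difference in cm² and the baseline mean that the 25% represents, so that both the 40 per group and the power at 35 per arm can be checked.

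The cost is wording in one section and a slightly less favourable power statement; no participants or procedures are added. If the sponsor prefers to keep the 30% allowance at 40 evaluable per arm, the target has to become 116 (58 per arm), and sections 5.1 and 5.3 and the synopsis total (116 + 30 = 146) would change with it.

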5.3 RECRUITMENT PROCEDURE

This trial will recruit from a population of postmenopausal women being treated at Austin Health for ER-positive breast cancer. Specifically, we will be recruiting from our multi-disciplinary Adjuvant Endocrine Breast Cancer Clinic that manages all women with breast cancer commenced on endocrine therapy.

We will take referrals of eligible women from Austin Health Physicians in private practice that are performing an analogous role to that of the public Adjuvant Endocrine Breast Cancer Clinic. If not already patients of Austin Health, these participants will receive an Austin Health unit record number. Health professionals who are known to have significant contact with patients who have breast cancer will be contacted to be made aware of the study and will be provided with information and the contact details of the investigators should they think a patient may fit the eligibility criteria.

The recruitment of 50 patients on AI and 50 DCIS/early breast cancer not requiring ET controls will be performed as per the sample size calculations (above).

In addition, we aim to recruit 30 patients receiving tamoxifen therapy for breast cancer so as to use this subset as a group with which to perform secondary endpoint analyses. Based on clinical experience and audit, this is the expected number of cases over the time course (18 months) of the recruitment phase of this study.

5.4 INCLUSION AND EXCLUSION CRITERIA

*INCLUSION CRITERIA

Women must meet all inclusion criteria in order to participate in the study.

- Postmenopausal women with oestrogen-receptor-positive, non-metastatic breast cancer (TxNxM0) based on documented pathological and radiological evaluation

- Age 50-85 years
- To commence adjuvant treatment with endocrine therapy as determined by treating oncologist/commenced endocrine therapy for no more than 8 weeks prior to recruitment
- OR
- Postmenopausal women with DCIS (any grade)/early breast cancer not requiring ET
- Endocrine therapy intended for at least 12 months
- ECOG 0 and 1
- Able to personally read and understand the Participant Information and Consent Form and provide written, signed and dated informed consent to participate in the study
- Able and willing to meet all protocol-required procedures and visits

Perimenopausal: absent cycles for 3-12months

Postmenopausal: absent cycles for 12 months

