Inclusion Criteria:	
Women must meet all inclusion criteria to participate:
 
 - Postmenopausal women with oestrogen-receptor positive non-metastatic breast cancer (TxMxM0) based on documented pathological and radiological evaluation - Ages 50-85 years (post-menopausal) 
Endocrine Therapy group:
 
 - Set to commence endocrine therapy as determined by the treating oncologist/commenced ET for no more than 8 weeks prior to recruitment 
OR
 
Control group:
 
 - Ductal carcinoma insitu (DCIS) – any grade not on ET/ Early stage, non-metastatic breast cancer not requiring ET - Treatment intended for at least 12 months - Eastern Cooperative Oncology Group (ECOG) 0 and 1 - Able to independently read and understand the participant information and consent form and provide written, signed and dated data informed consent to participate in the study - Able and willing to meet all protocol required procedures and visits
Exclusion Criteria:	
 - Cessation or switching ET during the 12 month study period

	
 - Previous hormone replacement therapy within 12 months of study recruitment - Glucocorticoid use (continuously for ≥ 2 weeks within the 6 months prior to screening) - Malignancy within the past 5 years including breast cancer requiring treatment (except non-melanoma skin cancers) - Established type 2 diabetes mellitus - Any disease which is likely to lead to serious illness or death within the study period - Self reported recreational drug use or alcohol dependence within 12 months of screening
Number of Planned Participants:	130
Statistical Methods:	
 • Longitudinal changes in the primary and secondary endpoints will be analyzed using paired-sample t-tests, generalised linear mixed models and generalised estimating equations and compared between patients with and without endocrine therapy • Adjustments will be made for age, comorbidities and baseline measurements
Subgroups:	
Tamoxifen Chemotherapy ER+ and HER2+ disease – commencing Herceptin as well as endocrine therapy Premature menopause/hysterectomy (<40yrs)

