3.2 SCIENTIFIC BACKGROUND

3.2.1 Oestrogen Deprivation Therapy in Postmenopausal Women with ER-positive Non-Metastatic Breast Cancer

(i) Oestrogen deprivation therapy: risk-benefit ratio and clinical implications

Breast cancer is the most common cancer to be diagnosed in women worldwide (1). In Australia it is estimated that 18,087 women will be diagnosed with breast cancer. This is approximately 50 women per day with roughly 70% classified as having oestrogen receptor positive (ER+) disease and require adjuvant endocrine therapy (2). Despite the large numbers of postmenopausal women diagnosed, advances in management has led to

significant increases in cancer survival, with non- breast cancer deaths comprising 73% of the total mortality (3). Of these, cardiovascular disease (CVD) remains the major contributor to mortality.

Aromatase inhibitor (AI) therapy for 5 years is standard treatment for early stage breast cancer and has been reported to prolong disease-free survival when compared with the selective oestrogen receptor inhibitor tamoxifen, in postmenopausal women (4, 5). The aromatase enzyme catalyzes the rate limiting step in the conversion of androgen to oestradiol (E2). AIs profoundly inhibit aromatase (>95%) and therefore cause “virtually complete” E2 deficiency, with reduction of plasma E2 levels to 3 pmol/l or less (the detection limit of the most sensitive assays), markedly below postmenopausal levels of 20-50 pmol/L (6). In high cancer-risk women, extending AI therapy to 10 years or extending tamoxifen therapy with a further 5 years of AI therapy may decrease rates of new and recurrent cancers (5). However, a decrease in high density lipoprotein by up to 15% at 2 years and an increase in low density lipoprotein by up to 16.5% at 12 months in postmenopausal women on AI therapy has been reported when compared with tamoxifen (7, 8). Therefore, in women exposed to extended AI therapy, the benefits of decreased recurrence must be weighed against the associated accumulated risks of metabolic syndrome and CVD.

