6. STUDY METHODOLOGY

6.1 STUDY VISITS

The following is a list of study interactions/visits and the data that will be collected. For the data collected please see section '6.3' for the specific measurements and techniques used.

- (i) **Screening of potential participants who consent:**
 - Medical interview and review of Austin Health medical file: demographic data (name, age, date of birth, hospital unit record number), and medical history and medication history sufficient to determine trial eligibility
 - For eligible participants, screening blood test and DXA scan will be used as baseline measurements if obtained within 8 weeks prior to entry into the trial
 - Patients are eligible for a baseline assessment if they plan to commence ET within 8 weeks of the assessment
- (ii) **Visit 1: Further baseline assessment of participants who are eligible based on screening**
 - Bloods tests
 - Medical Assessment and Anthropometric data
 - Questionnaires
 - DXA scan – measurements for bone mineral density/trabecular bone score, body composition and aortic calcification will be undertaken
 - EndoPAT peripheral arterial tonometry
 - Fibroscan
- (iii) **Visit 2: 6 months post recruitment**
 - Blood tests
 - Medical Assessment and Anthropometric data

- Questionnaires
- DXA
- EndoPAT peripheral arterial tonometry
- +/- Fibroscan (only if trends in liver function tests to suggest worsening steatosis or fibrosis)

(iv) **Visit 3: 12 months post recruitment**

- Blood test
- Medical Assessments and Anthropometric data
- Questionnaires
- DXA
- EndoPAT peripheral arterial tonometry
- Fibroscan

(v) **Visit 4: 24 months post recruitment**

- Blood test
- Medical Assessments and Anthropometric data
- Questionnaires
- DXA
- EndoPAT peripheral arterial tonometry
- Fibroscan

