6.2 STUDY SCHEDULE

Visit month	Event	Time (hrs)	Assessments	Standard Care	Dosage/Volume (blank where N/A)
Informed consent					
0	Screening visit	1	Medical interview	X	
0	Baseline Assessment	3	Medical assessment and Anthropometric data (1hr)	X	
			Blood tests (30min)	X	22.5ml standard care 20ml additional for study
			DXA** (30-45min) (whole body composition, trabecular bone score and abdominal aortic calcification)	X	0.06mSv
			EndoPAT (15 min)		
			Fibroscan (10min)		
			Questionnaires (10min)	X	

3	No visit	0	Blood tests	X	22.5ml standard care 20ml additional for study
6	Study visit 6 months from baseline	3	Medical assessment and Anthropometric data	X	
			EndoPAT		
			+/- Fibroscan		
			Questionnaires	X	
			Blood tests	X	22.5ml standard care 20ml additional for study
			DXA**		0.06 mSv
12	Study visit 12 months from baseline	3	Medical assessment and Anthropometric data	X	
			EndoPAT		
			Fibroscan		
			Questionnaires	X	
			Blood tests	X	22.5ml standard care 20ml additional for study
			DXA**	X	0.06 mSv
24	Study visit 24 months from baseline	3	Medical assessment and Anthropometric data	X	
			EndoPAT		
			Fibroscan		
			Questionnaires	X	
			Blood tests	X	22.5ml standard care 20ml additional for study
			DXA**	X	0.06 mSv

* Assessment without an 'X' are in addition to standard care

** Assessment of total body composition and abdominal aortic calcification are in addition to standard care, which involves scanning of the hip and spine

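### Women may enter up to 8 weeks after starting endocrine therapy with no pre-dose measurement required, so their baseline is normally an on-treatment value and their 12-month oestradiol change can be uninformative

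*Protocol*

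**What the plan says.** The eligibility rule in section 5.4 covers women about to start ET and women who "commenced endocrine therapy for no more than 8 weeks prior to recruitment". The Study Synopsis repeats it: "commenced ET for no more than 8 weeks prior to recruitment".

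Section 6.1 approaches baseline from the other side: "Patients are eligible for a baseline assessment if they plan to commence ET within 8 weeks of the assessment". It also allows earlier data to stand in: "screening blood test and DXA scan will be used as baseline measurements if obtained within 8 weeks prior to entry into the trial". It does not say that such data must precede ET, or that the scan must include body composition.

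Follow-up is counted from entry, for example "Visit 3: 12 months post recruitment". Section 6.2 counts from baseline. Neither counts from the first dose.

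The primary endpoint (section 4.3) is 12-month change in visceral adipose tissue (VAT), AI users against controls. The secondary endpoints include "Changes in sex steroids at 12 months". Section 3.2.1 reports AI treatment as causing "reduction of plasma E2 levels to 3 pmol/l or less", against postmenopausal levels of 20-50 pmol/L. Section 8.1 adjusts for age, comorbidities and baseline measurements.

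**The concern.** A change score measures a drug effect only if the first measurement precedes the drug. Women admitted through the second branch of section 5.4 have already been exposed, and nothing obliges the study to hold an unexposed value for them. Controls take no ET, so the problem is confined to the treated arms. Adjusting for the baseline value does not repair it, because that value may itself have been moved by treatment.

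Oestradiol is the most exposed measurement, because the protocol itself describes near-complete suppression on an AI. Section 4.1 also aims to relate oestradiol depletion to cardiovascular burden, and a change score from a suppressed baseline would record no depletion in a woman who is fully depleted. For VAT, the issue is an omitted early effect and unequal exposure at the visit labelled 12 months.

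These women may not be rare. Section 5.3 recruits specifically from a clinic that manages women who have been started on ET.

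**Working it through.** **1. Would a pre-dose value exist anyway?** Four places in the protocol bear on this.
- Section 5.5: no study procedure takes place before consent. A woman who consents while on ET has only standard-care data from before it.
- Section 6.2, footnote: "body composition and abdominal aortic calcification are in addition to standard care, which involves scanning of the hip and spine". A standard-care scan therefore carries no VAT value.
- Section 6.2, schedule: EndoPAT has no standard-care mark.
- Sections 6.3.3 and 9.1: sex steroids are measured by mass spectrometry on stored study aliquots. Section 6.3.9 lists a routine oestradiol, but that is not the assay set for this endpoint.

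So a pre-ET VAT, EndoPAT or mass-spectrometry oestradiol would normally not exist for her.

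**2. Exposure at the 12-month visit.** Take recruitment and Visit 1 as the same day.
- Baseline 8 weeks before ET: 52 - 8 = 44 weeks on drug.
- Baseline 8 weeks after ET start: 52 + 8 = 60 weeks on drug.

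The bounds are approximate, because no window is set between recruitment and Visit 1.

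**3. Oestradiol in AI users.** Inputs from section 3.2.1: E0 = 20 to 50 pmol/L without an AI, and 3 pmol/L (the upper limit given) on one.
- Pre-dose baseline: 3 - 20 = -17 and 3 - 50 = -47 pmol/L.
- Baseline already suppressed: 3 - 3 = 0.
- Share p of the arm suppressed at baseline: mean change = (1 - p)(3 - E0). With p = 0.5 (assumed), this gives -8.5 to -23.5 pmol/L.

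The protocol gives neither p nor the time to suppression.

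**4. VAT.** Let g(t) be the effect accrued by week t on drug.

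*Baseline at week +8.* The change score covers weeks 8 to 60. Its ratio to the true 52-week effect is [g(60) - g(8)] / g(52).
- Linear accrual: (60 - 8)/52 = 1.00, so nothing is lost.
- Exponential approach with half-life h: the ratio simplifies to 2^(-8/h). This gives 0.81 for h = 26 weeks, 0.65 for h = 13 and 0.50 for h = 8 (all assumed).

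*Baseline 8 weeks before ET.* The ratio is g(44)/g(52). Under linear accrual it is 44/52 = 0.846, about 15% less. For half-lives of 26, 13 and 8 weeks it is 0.92, 0.97 and 0.99.

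**5. What this could mean for power (illustration only).** Section 5.2 states 40 per group, SD 40 cm², 80% power and two-sided 0.05. It gives the difference as 25% with no mean. Reading that as 25 cm² (an assumption), n = 2(1.960 + 0.842)² × 40²/25² = 40.2, so 41. This matches the stated 40 closely, and 40 per group gives 79.8% power. If half the AI arm had a baseline at week +8:

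| Accrual (assumed) | Mean difference, cm² | Power at 40 per group |
|---|---|---|
| Linear | 25.0 | 79.8% |
| Half-life 26 weeks | 22.6 | 71.5% |
| Half-life 13 weeks | 20.7 | 63.7% |

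**The case against.** **The two sections may not conflict.** Section 5.4 has two branches, and the sentence in 6.1 can be read as the window for women yet to start. That is fair, but it leaves the other branch with no baseline rule at all. The allowance for screening data matches the 8-week limit in length, so some women on ET may have a pre-dose value, particularly if they consented before starting. Nothing requires it, and step 1 shows why it would usually be missing for the endpoints that matter here.

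**The VAT effect need not shrink.** A reader might infer that a baseline 8 weeks into treatment hides 8/52, about 15%, of a year's VAT change. The protocol does not support that. Visits run from recruitment, so this woman is still measured across 52 on-treatment weeks and loses nothing if accrual is linear. The 15% belongs to women whose baseline falls 8 weeks before ET. Loss in the on-treatment group needs a front-loaded effect, for which the protocol gives no shape.

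**The oestradiol point has limits.** A reader might extend the near-zero change to all sex steroids and to tamoxifen users. Section 3.2.1 supports it only for oestradiol on an AI, and only once suppression is complete. Nor does the oestradiol objective fail outright. The hypothesis in section 4.2 contrasts depletion with residual levels, and on-treatment levels still show that contrast between groups.

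**The screening scan.** Visit 1 DXA includes body composition, and nothing says that a hip-and-spine scan will replace it. The gap is only that section 6.1 sets no such condition on an earlier scan.

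**Feasibility.** Recruiting from this clinic makes the window understandable in an observational study, and applying the 8-week rule already requires knowing the ET start date. Both points stand. They make the fix cheap but do not make it unnecessary.

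**Conclusion.** The concern stands in a limited form. The protocol admits women already on ET without requiring a pre-dose measurement, and its baseline rule addresses only women yet to start. Followed as written, it normally yields on-treatment baselines for the former group, in the ET arms only.

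The firmest consequence is for oestradiol change in AI users: about 0 instead of -17 to -47 pmol/L in any woman suppressed at baseline. The arm mean falls in proportion to the share of such women. This rests on suppression being complete by baseline, which the protocol does not date.

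For VAT, the change score omits any effect before baseline. The net bias cannot be sized from the protocol. It may be nil, and it is attenuation only under front-loading, so it should not be stated as a fixed percentage. The spread of exposure, about 44 to 60 weeks, follows directly from the entry and baseline rules. Because a missed pre-dose measurement cannot be recovered later, this should be corrected.

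**What to change.** - Reconcile the Synopsis and section 5.4 with section 6.1 by defining baseline relative to ET start, with a rule for each branch of the entry criterion.
- Obtain study baseline bloods, DXA and EndoPAT before the first dose where this is possible without delaying anyone's treatment.
- Record the first-dose date and flag every on-treatment baseline.
- Restrict the oestradiol-change analysis in AI users to women with a pre-dose sample, and report on-treatment levels between groups for everyone.
- Give a sensitivity analysis for VAT limited to women with a pre-dose baseline. This and the previous rule can sit in the statistical analysis plan. The baseline definition and the flag belong in the protocol.
- Accept an earlier DXA as baseline only if whole-body composition was acquired.

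Do not re-time visits from the first dose for women with an on-treatment baseline. Their change score would then cover weeks 8 to 52, which is 44 weeks, and would create the 8/52 = 15.4% loss under linear accrual that the present timing avoids. Controls have no first dose, so follow-up intervals would also differ between arms.

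The cost is a short amendment, one added case report form field and a smaller set for the oestradiol-change endpoint. If half of the 50 planned AI users lacked a pre-dose sample (an assumption), 25 would remain before drop-out.
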